6.5 Secondary analysis

All time-to-event secondary analyses will be conducted similarly as for the primary analysis. They include:

- Time to clinical events (each defined by the WHO severity score or proxies to be defined)
 - Ambulatory status with no limitation of activities (WHO Ordinal Scale classification 1). This will be defined as subjects reporting COVID-19 related symptoms, clinical diagnosis of COVID-19 or positive test results, but reporting “No” limitation of activities due to their symptoms and no hospitalisation.
 - Ambulatory status with limitation of activities (WHO Ordinal Scale classification 2). This will be defined as subjects reporting COVID-19 symptoms, clinical diagnosis of COVID-19 or positive test results and reporting “Yes” to having their usual activities limited being limited due to their symptoms, but no hospitalisation.
 - Hospitalised mild disease (WHO Ordinal Scale classifications 3 and 4). This is defined as being hospitalised without being admitted to the ICU or without ventilation.
 - Hospitalised severe disease (WHO Ordinal Scale classifications 5 to 7). This is defined as being hospitalised with either admittance to the ICU and/or receiving ventilation.
 - Death (WHO Ordinal Scale classification 8)

Furthermore, to explore key factors (eg. PPE, HCW and healthcare facility characteristics, underlying co-morbidities, household history and COVID-19 exposure) that potentially modify the risk of COVID-

19 among HCWs, the following analysis will be undertaken. For the covariates remaining in the final model of the primary analysis, one covariate will be removed at a time and will be tested using a likelihood ratio test to determine their association with the primary outcome.

Finally, as described in section 3.5.2, the type of prophylactic treatments (Chloroquine, Hydroxychloroquine, Azithromycin, Lopinavir/ritonavir, Ivermectin, others) will be characterized by dose, frequency and duration, overall and by country/region/site. To note, prophylactic treatment use will be defined by relevant indication from 'prophylactic treatment' section of the survey; in addition, if there is an indication of drugs in 'concomitant medications' section that are also listed but not selected under 'prophylactic treatment' section, those indications will be added too.

Other derived variables such as time in hospitalization will be analyzed via generalized mixed effect models.

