5 Determination of Sample Size

The targeted sample size of approximately 10,000 HCWs assumes that 20% of the study population are non-exposed to potential prophylactic treatments, with a baseline risk of SARS-CoV-2 infection in the study period of 10% (for unexposed: not treated with potential prophylactic treatment). A total of N=10,000 allows for 80% power to identify an effect size of Relative Risk = 0.78.

If these sample sizes are not reached with respect the study population being exposed/non-exposed to potential prophylactic treatments, the relative risk may be detected with lower power or it may not be statistically significant. However, the secondary objectives can still be examined.

6 Statistical analysis

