6.1 Overview

All statistical analyses will be conducted using R (version 1.3.1093), unless otherwise specified.

For all descriptive analyses, categorical variables will be summarized by number of observations and percentage (%). Percentages will be rounded to one decimal place and will be based on available observations (known values), unless otherwise specified. Continuous variables will be summarized using descriptive statistics (n, mean, with standard deviation; minimum, first quartile, median, third quartile,

and maximum). Outliers will be included in descriptions as part of presenting ranges and percentiles (25th and 75th). The mean and SD will be rounded to one decimal place.

All statistical tests will be two-sided and at 5% level of significance.

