6.3.7 Prophylactic medications

Prophylaxis usage of subjects included in the study will be descriptively summarized for HCWs with and without COVID-19 infection (see Table 8.2.8 in the appendix):

A stacked bar chart will be used to display the prophylaxis usage during the follow-up period. The x-axis will be dates of survey responses and the stacked bars will be grouped by yes/no (corresponding to prophylaxis use at specific dates). This will be done separately for HCWs infected with COVID-19 and those uninfected. The stacked bar charts can be used to compare prophylaxis use among infected/uninfected HCWs over time. This will be done for “any prophylaxis use” and if sample if sample sizes permit they will

be presented for the major individual prophylaxis treatments (ie. azithromycin, chloroquine/hydroxychloroquine, ivermectin, lopanavir).

Prophylaxis usage pre- and post- first date of COVID-19 exposure will also be described, stratified further by COVID-19 infection status.

- Types, intake frequency, and doses of prophylactic treatments
 - Treatment name
 - Date started
 - Date stopped
 - Dose (intake)
 - Duration of treatment
 - Dose frequency and dosing interval
 - Status (stopped/ongoing)
 - Reason for stopping (not available/side effects/expense/other)
 - Number of missed doses and reason (not available/side effects/expense/other)

For HCWs with COVID-19 at entry: prophylaxis treatments used before the COVID-19 infection date will be described.

For HCWs with COVID-19 at follow-up: prophylaxis treatments used over the entire follow-up time available in the data cut. In addition, prophylaxis treatments used within 2 or 4 weeks (TBD) before COVID-19 infection date will be described.

For HCWs with no COVID-19 infection at any time: prophylaxis treatments used over the entire follow-up time available in the data cut. In addition, prophylaxis treatments used within 2 or 4 weeks (TBD) prior to the data cut date will be described.

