6.4 Primary analysis

6.4.1 Frailty model: mixed effect Cox regression

For the time to COVID-19 infection outcome, both crude and adjusted hazards ratios will be estimated for time to COVID-19 infection with respect to prophylaxis use. The primary objective of this analysis is to assess the association between prophylactic treatments and the reduced risk of SARS-CoV-2 infection in HCWs caring for COVID-19 patients. A mixed effect Cox regression model (ie. frailty model) will be used to estimate adjusted hazard ratios. This method will allow the utilization of both the repeated measures gathered from each HCWs surveys, as well as the incorporation of time-varying covariates of interest such as PPE usage and COVID-19 exposure. Each subject will be included as a random effect. Both time-fixed and time-varying covariates will be included in the model. Covariates will be assessed using a univariate model, any covariates with a p-value less than 0.20 will be included in a multivariate model. A backward stepwise process will then be completed, where the covariates with largest p-value are removed one at a time until all covariates that remain are significant at the 0.10 level. The time-fixed covariates, healthcare facility and country will be included in the model regardless of their significance level. Including the healthcare facility and country covariates will make each healthcare worker's COVID-19 outcome conditionally independent on the background COVID-19 incidence occurring within each subject's healthcare facility and country. A list of additional covariates to be considered can be found in Table 5.4.1. For each subject in the control group, the index date (ie. time of first known exposure to COVID-19 patients) will be used as time zero. For HCWs that are treated with prophylaxis at any time their index date will be 7 days after initiation of treatment. Having an index date near treatment initiation will prevent the introduction of survivorship bias into the analysis.

Table 5.4.1 Model Covariates

Time-fixed/Time-varying Covariate	Covariate Name
Time-fixed Covariates	Healthcare facility, Country, Age, Biological Gender, BMI, Smoking status, Ethnicity, Blood type, Primary work location, Type of healthcare worker, Medical history

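### The hospitalisation and death analyses reuse an ever-treated exposure with no pre-infection cut-off, so listed drugs first taken after infection can move events out of the untreated comparator

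*SAP*

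**What the plan says.** SAP 6.5 covers time to ambulatory disease with and without limitation of activities, mild and severe hospitalisation, and death. It states: "All time-to-event secondary analyses will be conducted similarly as for the primary analysis".

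The primary analysis in SAP 6.4.1 starts controls at first known exposure to COVID-19 patients. For the other group: "For HCWs that are treated with prophylaxis at any time their index date will be 7 days after initiation of treatment". Prophylaxis is not among the time-varying covariates in Table 5.4.1.

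SAP 3.5.2 takes exposure from the prophylaxis section of the survey and adds listed drugs reported only as concomitant. SAP 3.6.5 repeats this for five named drugs. Neither sets a condition on start date or reason for use.

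A pre-infection cut appears only in the descriptive SAP 6.3.7, for one group: "For HCWs with COVID-19 at entry: prophylaxis treatments used before the COVID-19 infection date will be described". For the adjacent column of Table 8.2.8: "For HCWs with COVID-19 at follow-up: prophylaxis treatments used over the entire follow-up time available in the data cut". A further description, limited to 2 or 4 weeks before infection (length undecided), is planned for those follow-up cases.

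Protocol 8.7.1 leaves it to the SAP to define exposure attributable to a given outcome. Protocol 8.7.4 promises rules, agreed with the Scientific Advisory Committee, for assigning outcomes to exposure time. The SAP contains neither.

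**The concern.** The secondary outcomes follow an HCW past infection. The interval between infection and hospitalisation is when a listed drug may be taken because the HCW is ill. The survey has a prophylaxis section and a section for medicines taken for reasons other than COVID-19, but the listed variables include no place for COVID-19 treatment and no reason for starting. A drug begun after infection and reported in either section is counted as prophylaxis.

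An infected non-user then changes group because of the infection. If sicker HCWs are more likely to start a drug, the comparator loses its severe cases selectively, and the hospitalisation result partly describes treatment by indication.

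The planned checks do not remove this. SAP 6.6 and 7.6 select on infection status at index date or entry, or on available serology, not on drug start relative to an infection during follow-up. SAP 6.6 also repeats the secondary analyses in HCWs who already had COVID-19 at entry, where any drug started after entry follows infection.

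**Working it through.** **Inputs from the documents.** SAP 5 gives N = 10,000 and "assumes that 20% of the study population are non-exposed to potential prophylactic treatments", so 2,000 non-users and 8,000 users, with a 10% infection risk in non-users. SAP 6.1: "All statistical tests will be two-sided and at 5% level of significance".

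**The plan's own figure.** SAP 5: "A total of N=10,000 allows for 80% power to identify an effect size of Relative Risk = 0.78". Expected infections are 2,000 × 10% = 200 and 8,000 × 7.8% = 624, total 824. Schoenfeld's formula gives √(824 × 0.2 × 0.8) × |ln 0.78| − 1.96 = 11.48 × 0.2485 − 1.96 = 0.893, or 81.4% power, close to the stated 80%. A pooled two-proportion test gives 87.7%. The point does not depend on which was used; only the group sizes and the 10% risk carry forward.

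**Assumptions (not in the documents).** The drug is inert, and 5% of infections lead to hospitalisation. A share q of hospitalised non-users, and q/2 of other infected non-users, start and report a listed drug after infection.

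**Head count.** Non-users: 2,000 × 10% × 5% = 10 hospitalised and 190 other infections. Users: 8,000 × 10% × 5% = 40 hospitalised. The true RR is 1.00. After reclassification:

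- comparator risk = 10(1 − q) / (2,000 − 10q − 95q)
- treated risk if moved events count as treated = (40 + 10q) / (8,000 + 10q + 95q)
- treated risk if moved events precede time zero and drop out = 40 / (8,000 + 95q)

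| q | Comparator | Treated, counted | RR | Treated, dropped | RR |
|---|---|---|---|---|---|
| 10% | 9/1,989.5 | 41/8,010.5 | 1.13 | 40/8,009.5 | 1.10 |
| 20% | 8/1,979 | 42/8,021 | 1.30 | 40/8,019 | 1.23 |
| 40% | 6/1,958 | 44/8,042 | 1.79 | 40/8,038 | 1.62 |

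**Second set of assumptions.** With 10% of infections hospitalised and the same q for all infected non-users, the comparator keeps 18, 14 and 10 of its 20 hospitalisations at q = 10%, 30% and 50%. The RR is 1.12, 1.48 and 2.11 (counted) or 1.10, 1.38 and 1.88 (dropped). Assuming 5% or 15% hospitalised gives the same RRs.

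**When the direction would turn.** Let s be the share of hospitalised, and r the share of other infected, non-users who move. If moved events drop out, RR = 1 when 40/(8,000 + 190r) = 10(1 − s)/(2,000 − 10s − 190r). This reduces to s(7,960 + 190r) = 950r, so s ≈ 0.12r. If they count as treated, s ≈ 0.10r. The hospitalisation RR exceeds 1 unless hospitalised non-users start and report a listed drug at under about an eighth of the rate of other infected non-users.

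**Effect of the shifted time zero.** A Cox simulation of the SAP rule assumed 10% of infections hospitalised 5 to 12 days after infection, prophylaxis started up to 30 days before first exposure, and listed drugs started 1 to 10 days after infection. With 100 runs per setting, the median HR was 0.92, 0.95, 1.27 and 1.69 at q = 0, 10%, 30% and 50%. The 0.92 at q = 0 is a separate downward effect of the shifted clock. About 5 hospitalisations at q = 30%, and 8 at q = 50%, fell before time zero and were lost.

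**Death.** If drugs taken in the final illness are never reported, fatal cases stay in the comparator and only survivors move. Then RR = 8,000/(8,000 + 200q) × (2,000 − 200q)/2,000, which is 0.99, 0.96 and 0.94 at q = 10%, 30% and 50%.

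**With a pre-infection cut.** All comparator hospitalisations stay, and the head-count RR is (40/8,000)/(10/2,000) = 1.00. The simulated median HR was 0.97 to 1.08. That run also started no one's clock before first exposure, so it does not isolate the date cut.

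**The case against.** The SAP does not say that drugs taken to treat COVID-19 count as prophylaxis, and a reader should not infer that it does. Protocol 6 defines prophylactic treatments as those meant and used to prevent infection. An HCW answering the two drug sections literally would report therapeutic use in neither, so q is the share who both start and report such a drug. No figure in the documents supports any particular value. This limits the size but not the gap: the SAP never puts the definition into operation, and it adds concomitant reports whatever their purpose.

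A reader might infer that prophylaxis would look harmful for death as well. The documents do not support that. SAP 3.5.2 takes mortality from the secondary contact, and Appendix 2 of the protocol asks that contact nothing about drugs. Protocol 8.9 and SAP 7.4 say hospitalisation reporting also leans on the contact, which weakens the effect there. However, Appendix 2 has the HCW report hospitalisation too.

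A reader might also infer that SAP 6.3.7 ignores pre-infection use in follow-up cases. It does not, since a 2-or-4-week description is planned as an addition. What remains is that the main description for those cases spans all follow-up beside a pre-infection column for entry cases.

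The head count overstates the HR at low q, because it leaves out the shifted clock: the simulated HR at q = 10% was 0.95. With 10 and 40 events, the standard error of the log RR is √(1/10 + 1/40) = 0.354, so a 95% interval around 1.0 runs from about 0.50 to 2.00. A small q would be hidden in noise.

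Finally, the SAP 6.5 wording creates no new exposure rule; the source is the grouping in 6.4.1. That is correct, and the fix belongs in both places.

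**Conclusion.** The concern holds for hospitalisation. As written, the rule lets a drug first taken after infection move a non-user, with any hospitalisation, out of the comparator, and no planned check removes this. The bias runs against prophylaxis. For an inert drug, the head-count RR is about 1.1 at q = 10%, 1.2 to 1.3 at q = 20% and 1.6 to 1.8 at q = 40%. In the simulation the shifted time zero offset this at q = 10% but not at q = 30% or more.

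The sizes rest on assumed values of q and, for the event counts, of the hospitalised share. For death the direction is uncertain and the head-count effect small (0.94 to 0.99 if terminal drug use goes unreported). The SAP should have carried over the exposure-timing rules that protocol 8.7.1 and 8.7.4 call for.

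**What to change.** State in SAP 3.5.2, 6.4.1 and 6.5 that, for every outcome, prophylaxis status counts only drugs started before the infection date. Define that date as when the primary-outcome definition is first met: the test date, onset of the symptoms finally adopted as qualifying, or the survey week of a reported clinical diagnosis. Onset of any listed symptom should not be used. The list includes headache and runny nose, SAP 6.3.9 has yet to settle which symptoms qualify, and prophylaxis begun after an unrelated symptom would be lost.

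A later start does not make an HCW treated or reset time zero, and is reported in its own row. In Table 8.2.8, use a pre-infection window for follow-up cases, as for entry cases.

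The cost is SAP wording and a date comparison, but not every date exists. Start dates are listed for the prophylaxis section only. Appendix 2 of the protocol lists concomitant drugs as yes/no, and no clinical-diagnosis date is listed. Date concomitant drugs by the first survey week that reports them, and add a sensitivity analysis excluding concomitant-only reports and starts close to onset. Weekly, approximate or imputed dates will still misclassify some starts near onset.

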8.7.4 Primary Analysis

A standard pharmaco-epidemiological inferential analysis will be conducted treating the registry data as a cohort with dynamic exposure to both prophylactic treatment and to COVID-19 infected patients and adjusting for potential confounding.

Both crude and adjusted hazards ratios will be estimated for prophylactic regimens of interest and any observed impact on the risk of infection among HCWs based on all statistical inferential models will be reported.

Outcomes will be adjudicated to exposure time based on prior decision rules agreed with the SAC. Hazards for each subject-week will be compared and adjusted for exposure to prophylaxis over time, exposure to COVID-19 positive patients over time and to other covariates, accounting for subject-level clusters. Repeated time-to-event analyses with competing risk will be carried out.

Handling of missing data and unexplained drop-outs will be discussed with the SAC. Interaction terms to be considered will also be discussed with the SAC and clinicians.

Matching or other balancing methods such as estimated propensity score matching, inverse probability weighting or marginal structural methods, or alternative methods, will be considered to potentially address the identified biases and allow for evaluation of association.

In case the number of infection cases is lower than anticipated to allow for such analyses, matched case-control analyses will also be considered.

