3.5.2 Secondary Outcomes

For the following outcomes, infection status will be defined as per the composite primary outcome. Ambulatory status and hospitalisation will be based on responses to the relevant questions in the survey. Mortality will be based on the survey response of each subject's secondary contact. Prophylactic treatment will be based on relevant questions from healthcare worker's surveys.

- Occurrence of SARS-CoV-2 uninfected HCWs
- Occurrence of SARS-CoV-2 infection with ambulatory status and no limitation of activities. This will be defined as subjects reporting COVID-19 related symptoms, clinical diagnosis of COVID-19 or positive test results but reporting "No" limitation of activities due to their symptoms and no hospitalisation.
- Occurrence of SARS-CoV-2 infection with ambulatory status and limitation of activities. This will be defined as subjects reporting COVID-19 symptoms, clinical diagnosis of COVID-19 or positive test results and reporting "Yes" to having their usual activities limited being limited due to their symptoms, but no hospitalisation.
- Occurrence of hospitalisation due to COVID-19 illness with mild disease. This is defined as being hospitalised without being admitted to the ICU or without ventilation
- Occurrence of hospitalization due to COVID-19 illness with severe disease. This is defined as being hospitalised with either admittance to the ICU and/or receiving ventilation.
- Occurrence of all-cause mortality

- Type of prophylactic treatments (Chloroquine, Hydroxychloroquine, Azithromycin, Lopinavir/ritonavir, Ivermectin, others) by dose, frequency and duration, overall and by country/region/site. To note, prophylactic treatment use will be defined by relevant indication from 'prophylactic treatment' section of the survey; in addition, if there is an indication of drugs in 'concomitant medications' section that are also listed but not selected under 'prophylactic treatment' section, those indications will be added too.

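### Separate hazard ratios for WHO state 1, state 2 and mild hospitalisation have no fixed direction of benefit, and the SAP does not say how a worker is assigned to a state

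*SAP*

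**What the plan says.** SAP section 6.5 introduces the severity outcomes as "Time to clinical events (each defined by the WHO severity score or proxies to be defined") and sets the method in one sentence: "All time-to-event secondary analyses will be conducted similarly as for the primary analysis". The primary analysis in SAP 6.4.1 is a mixed-effect Cox model, so each state gets its own hazard ratio.

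The three lower states are defined by what they exclude:

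- **State 1**, listed as "Ambulatory status with no limitation of activities (WHO Ordinal Scale classification 1"), is infection with no "limitation of activities due to their symptoms and no hospitalisation".
- **State 2** is infection with "having their usual activities limited being limited due to their symptoms, but no hospitalisation".
- **Mild hospitalisation**: "This is defined as being hospitalised without being admitted to the ICU or without ventilation". I read this as neither ICU nor ventilation, in line with Protocol 8.3.1.

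SAP 3.5.2 uses the same definitions. Severe hospitalisation does not exclude later death. Neither document plans a state-or-worse endpoint, an ordinal model or a multistate model. SAP 6.3 displays the distribution of scores over time, and shell Table 8.2.2 counts workers in each state by prophylaxis use.

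**The concern.** State 1 is worse than being uninfected and better than everything above it. A worker whose illness is held at state 1 instead of reaching state 2 or hospital adds a state 1 event, so a real severity benefit pushes that hazard ratio up. State 2 and mild hospitalisation gain cases from above and lose them to below, so their ratios can also move either way. The SAP does not say how a ratio above 1 for these states should be read.

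There is also a dating problem. The absence of hospitalisation cannot be known on the day a worker first reports state 1 or 2. A worker with no limitation in week 2 who is admitted in week 4 is either an event that later contradicts its own definition, or an event removed by using future data.

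The registry aims to inform policy on prophylactic use. A published hazard ratio above 1 for unrestricted infection could be taken as harm when the agent has only made illness milder.

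**Working it through.** **The plan's own figure.** The plan gives no figure for severity. Its sample size inputs (SAP section 5) are N = 10,000, 20% unexposed, 10% risk of infection in the unexposed, and relative risk 0.78 with 80% power. Expected events are 2,000 × 0.10 + 8,000 × 0.078 = 824. By the Schoenfeld formula with two-sided 5%, √(824 × 0.2 × 0.8) × |ln 0.78| − 1.96 = 11.48 × 0.2485 − 1.96 ≈ 0.89, which gives 81.4% power and agrees with the stated 80%. (A two-proportion formula gives 87.7%; this does not affect the point.)

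**State 1 under a worst-state rule.** Let s be the share of control infections that peak at state 1, f the factor by which treatment multiplies progression beyond state 1, and R the infection relative risk. Then

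state 1 ratio = R × [1 − (1 − s) × f] / s.

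The documents give neither s nor f. I assume f = 0.5 and s = 40%, 60% or 80%. R is 1 or the planned 0.78. The ratio for limitation of activities or worse is R × f.

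| s | State 1 ratio, R = 1 | State 1 ratio, R = 0.78 | Limitation or worse, R = 1 / R = 0.78 |
|---|---|---|---|
| 40% | 0.70/0.40 = 1.75 | 1.365 | 0.50 / 0.39 |
| 60% | 0.80/0.60 = 1.33 | 1.04 | 0.50 / 0.39 |
| 80% | 0.90/0.80 = 1.125 | 0.8775 | 0.50 / 0.39 |

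These are ratios of risks. With 10% infection risk they lie close to hazard ratios. The state 1 ratio exceeds 1 only if R is above s / [1 − (1 − s) × f], which is 0.57, 0.75 and 0.89 for the three rows.

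**State 2 and mild hospitalisation.** Assume control infections peak at 50% state 1, 35% state 2, 10% mild hospitalisation, 4% severe and 1% death.

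- An agent that halves severe disease and death, moving those cases to mild hospitalisation, gives (0.10 + 0.5 × 0.05)/0.10 = 1.25 for mild hospitalisation.
- An agent that halves all hospitalisation and death, moving those cases to state 2, gives (0.35 + 0.5 × 0.15)/0.35 = 1.21 for state 2.
- An agent that halves everything beyond state 1, moving those cases to state 1, gives 0.50 for both.

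All three agents are beneficial, and the single-state ratios point in different directions.

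**Chance of a significant result in the wrong direction.** At 2,000 : 8,000, with no effect on infection and worse states cut by 30% to 50%, a crude two-proportion approximation for state 1 gives 72% to 99% if half of control infections are state 1 (for example 5.0% against 6.5% or 7.5%). It gives 26% to 59% if 70% are (7.0% against 7.9% or 8.5%). Dropout and covariate adjustment are ignored.

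**The first-report rule.** A small Cox simulation (N = 10,000, 10 replicates per scenario) used the five-state mix above, worse states halved and R = 1. It counted any report of state 1 as the event.

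| Worse cases that first pass through state 1 | State 1 hazard ratio |
|---|---|
| None | 1.51 |
| Half | 1.20 |
| All | 0.98, equal to the infection hazard ratio |

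The result therefore depends on a rule the SAP leaves open.

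**The case against.** The strongest reply is that a time-to-event outcome built from weekly surveys is naturally read as first report of the state. If every infected worker passes through state 1, its hazard ratio is simply the infection hazard ratio. This stands as a limit on the point. But full pass-through is needed for the distortion to vanish, and the definitions describe subjects while Table 8.2.2 tabulates persons, which suggests one class per worker.

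Three stronger conclusions are tempting, and the documents do not support them.

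- *That a milder-illness effect always reads as harm at state 1.* This requires a worst-state or partial pass-through rule and an effect mainly on severity. With the planned relative risk and 80% peaking at state 1, the ratio is 0.88: below 1, but weaker than the infection effect of 0.78.
- *That the plan has no other evidence on severity.* SAP 6.5 also analyses death, severe hospitalisation and time in hospital. SAP 6.7 repeats the primary analysis on hospitalised cases only. SAP 6.3 compares weekly hospitalisation and death rates by prophylactic use, and a shift between states would show in Table 8.2.2. Three of the six clinical secondary outcomes are affected, not the whole set.
- *That the missing competing-risk model is the cause.* Protocol 8.7.4 states "Repeated time-to-event analyses with competing risk will be carried out", and SAP 6.4 and 6.5 do not carry this over. That is a separate discrepancy. A competing-risk model would not help here, because the cause-specific and subdistribution hazards of state 1 rise too.

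It is also fair to say that neither secondary objective is about severity, although Protocol 8.1 says the association will be measured on the WHO scale.

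**Conclusion.** The point holds in a limited form. Hazard ratios for state 1, state 2 and mild hospitalisation, as SAP 6.5 defines them, cannot be read as benefit or harm without knowing the assignment rule and what happens in the neighbouring states. The figures in the working rest on worst-state classification, assumed severity shares and an assumed halving of progression. They show what the planned analysis could produce and do not predict what it will.

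The primary outcome and death are unaffected, and severe hospitalisation largely so, because its definition does not exclude death. This is a cheap improvement to the secondary analyses and no threat to the main result.

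**What to change.** In SAP 6.5, replace the single-state hazard ratios for state 1, state 2 and mild hospitalisation with cumulative endpoints, each with one direction of benefit:

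- time to limitation of activities or worse, including hospitalisation and death;
- time to any COVID-19 hospitalisation or death;
- time to severe hospitalisation or death.

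Report them alongside the infection and death analyses already planned. Date each event at the first survey that meets the threshold, so no future information is needed. Keep the single states as descriptive counts of the worst state reached by the end of follow-up, and say so in SAP 3.5.2 and Table 8.2.2.

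The limitation-or-worse endpoint is the main addition; the hospitalisation endpoint is close to the hospitalised-only sensitivity analysis. The cost is SAP wording and recoding of variables already collected. The downside is that single-state hazard ratios are no longer reported, and the new endpoints are nested, so their results are not independent.

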2.2 Secondary objectives

- To characterize the type of potential prophylactic treatments, by dose and duration, overall, and by country/region/site.
- To explore the key factors (for example, use of PPE, HCW and healthcare facility characteristics, underlying co-morbidities, household history and COVID-19 exposure) modifying the risk of COVID-19 among HCWs.

[figure not shown]
3 Study overview

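### Apart from facility and country, the SAP 6.5 risk-factor tests are run only on covariates already retained at p<0.10 in the same data, and dropped factors such as PPE are promised no adjusted estimate

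*SAP*

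**What the plan says.** The second secondary objective (SAP 2.2, also Protocol 7.2) reads in part "To explore the key factors (for example, use of PPE, HCW and healthcare facility characteristics, underlying co-morbidities, household history and COVID-19 exposure". PPE is named first, and the aim is worded as exploration.

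SAP 6.4.1 builds the primary model in two data-driven steps. First, "any covariates with a p-value less than 0.20 will be included in a multivariate model". Then covariates are eliminated backward "until all covariates that remain are significant at the 0.10 level". There is one exemption: "healthcare facility and country will be included in the model regardless of their significance level". A note under Table 5.4.1 adds that only one of a set of highly correlated variables will enter. It gives no threshold.

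SAP 6.5 then turns to the risk factors. "For the covariates remaining in the final model of the primary analysis", it says, "one covariate will be removed at a time and will be tested using a likelihood ratio test" for association with the primary outcome. SAP 6.1 applies a two-sided 5% level to every test. No adjustment for selection or multiplicity is stated. SAP 6.4.1 promises hazard ratios for prophylaxis use; for the risk factors, SAP 6.5 promises a test and no estimate.

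Separately, SAP 6.3.3 to 6.3.5 and 6.3.8 describe household, patient-exposure, medical-history and PPE variables by infection status. Table 8.2.2 sets the outcomes against PPE use, and Table 8.2.9 gives PPE use by infection status. None of this depends on what the model retains.

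**The concern.** A covariate that went through backward elimination is in the final model because it was significant at 0.10. Removing it and testing the change in likelihood asks nearly the same question of the same data and outcome, and the answer is then judged at 5% as if it were new.

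The other half of the problem is what drops out. The four PPE items are all open to elimination. One that fails has no place in the SAP 6.5 analysis, so the plan promises no hazard ratio or interval for it adjusted for patient contact, household exposure or work location. The registry is meant to inform prevention policy, so an absent estimate for masks or eye protection matters. A reader can too easily take absence from the model as evidence of no effect.

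**Working it through.** **1. The plan's own figure.** No figure is given for the risk-factor objective. SAP 5 states 80% power for the primary objective: N = 10,000, 20% unexposed, 10% baseline risk, relative risk 0.78. The implied events are 2,000 × 0.10 + 8,000 × 0.078 = 200 + 624 = 824. Reading the relative risk as a hazard ratio, Schoenfeld's formula gives Φ(√(824 × 0.2 × 0.8) × |ln 0.78| − 1.96) = Φ(11.48 × 0.2485 − 1.96) = Φ(0.893) = 81.4%, which agrees. A pooled two-proportion formula gives 87.7%. This step is used only for the 824 events.

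**2. Candidates.** Table 5.4.1 lists 11 time-fixed and 11 time-varying covariates. Taking out facility and country leaves 9 + 11 = 20 open to selection, of which 4 are PPE items.

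**3. A null covariate that survives.** Under the null, P(p<0.05 given p<0.10) = 0.05/0.10 = 50%. Simulating the full sequence (univariate 0.20, backward 0.10, then a 5% test) with 20 independent null covariates gave:
- 50.3% of survivors significant in a large-sample Gaussian version;
- 49.8% using actual likelihood ratio tests in logistic models (10,000 subjects, risk 8.24%, 1,500 runs), with 1.97 covariates retained per run;
- 69% in the Gaussian version when all candidates were correlated at 0.3.

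**4. Is it the same test?** In the logistic runs the likelihood ratio p-value differed from the Wald p-value at the last backward step by at most 0.0004.

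**5. Count of false positives, all 20 null.** With selection: 20 × 0.10 × 0.50 = 1. With one full model: 20 × 0.05 = 1. The chance of at least one is 1 − 0.95^20 = 64% for the full model with independent factors, and 63% to 66% in the simulations with selection. Selection does not raise the count.

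**6. Chance that a protective PPE item is dropped.** For an uncorrelated binary item with always-use share q, z = |ln HR| × √(824 × q(1 − q)), and P(dropped) is about Φ(1.645 − z). For HR 0.80:
- q = 0.5: z = 0.2231 × √206 = 3.20; Φ(−1.56) = 6%.
- q = 0.9: z = 0.2231 × √74.16 = 1.92; Φ(−0.28) = 39% (40% in simulation).

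Simulated values at 50% / 90% always-use:

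| Assumed HR | Uncorrelated | Four PPE items correlated at 0.6 |
|---|---|---|
| 0.90 | 55% / 76% | 68% / 83% |
| 0.85 | 25% / 58% | 41% / 71% |
| 0.80 | 6% / 40% | 19% / 54% |
| 0.70 | 0% / 8% | 1% / 21% |

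**7. What a dropped item could have shown.** At 90% always-use the standard error is 1/√74.16 = 0.116. An item just missing p = 0.10 has HR exp(−1.645 × 0.116) = 0.83, with 95% CI 0.83 × exp(±1.96 × 0.116), about 0.66 to 1.04. That is far from evidence of no effect.

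**The case against.** The strongest reply is that selection does not add false positives: the expected count is about 1 in 20 either way, as step 5 shows. That stands. The 50% figure is conditional on survival. It describes how far a survivor's p-value can be trusted, not how many errors the analysis makes. The all-null setting is also a benchmark rather than a forecast, since household diagnosis and patient contact plausibly do affect risk.

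A reader might infer that dropped PPE items would go unreported, or that every test in SAP 6.5 is circular. The documents support neither. Crude PPE, household, exposure and comorbidity results are always tabulated, and a univariate model is fitted for each candidate, although reporting it is not promised. Facility and country reach the test without passing a significance screen.

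Some covariates have several levels, such as PPE use, blood type and type of worker, and the SAP does not say whether elimination uses per-level or joint p-values. If per-level, a joint likelihood ratio test adds something, so the near-identity in step 4 is shown only for one-parameter covariates.

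The objective is exploratory, which lowers the weight of the point but does not make the p-values valid. Finally, a full model has a price: PPE items and the three household items may be collinear, facility is nested in country, and the protocol itself plans for low event numbers. The fix has to deal with these.

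**Conclusion.** The point holds as a cheap improvement to an exploratory analysis. For the 20 selectable covariates, the SAP 6.5 p-values come after selection on the same data and cannot be read at 5%; about half of null survivors would look significant. For dropped factors, what is missing is a promised adjusted hazard ratio and interval, not all reporting. It would go too far to say that the plan inflates the number of false findings.

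The dropout risk depends on assumptions that the documents do not give: the PPE hazard ratio, the share always using each item, and the correlation between items. Over the range examined it runs from near 0% to above 80%. The 824 events assume that the sample-size premises hold. The simulations used one parameter per covariate, fixed rather than time-varying values, and no frailty term.

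**What to change.** In SAP 6.5, replace the leave-one-out test on survivors with one pre-specified model containing the factors that the objective names: PPE, patient exposure, household history, comorbidity, and worker and facility characteristics.

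- Form composites or collapse categories for collinear items without reference to the outcome.
- Specify facility and country so that both can be estimated, for example with facility as a random effect.
- Report the adjusted hazard ratio and 95% CI for every factor whatever its p-value, labelled exploratory and with no multiplicity claim.

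A null factor's p-value then has its nominal 5% error rate, and no named factor lacks an adjusted result. The change does not cure multiplicity: 20 independent null factors still give a 64% chance of at least one p<0.05, so the intervals should lead the report. Nor does it create power. At HR 0.80 with 90% always-use and uncorrelated items, full-model power is about 49%.

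The cost is SAP wording and one more model fit on data already collected. Intervals will be somewhat wider for correlated items or if events are few.
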